5.7.4. ECG

TriPLICATE 12-lead electrocardiograms (ECG) are to be collected at the timepoints specified in Schedule of Activities. The continuous (non-categorical) ECG test measured in triplicate includes heart rate, PR interval, QRS interval, QT interval, QTc interval using Fridericia's formula (QTcF) and RR interval. Each triplicate ECG is also interpreted as "normal", "abnormal" or "not evaluated". The number and percentage of participants with shifts from normal to abnormal will be summarized by treatment group. All postbaseline data will be used to identify abnormalities, regardless of whether a scheduled or unscheduled visit.

The mean of the triplicate continuous ECG parameter values at each nominal timepoint will be used for the analyses. If any triplicate within a nominal timepoint is abnormal, the interpretation will be counted as abnormal once for that nominal timepoint.

Actual values and change from baseline for the continuous (non-categorical) ECG parameters will be descriptively summarized by timepoint. Baseline for these analyses will be the mean of the replicate values from predose Day 1. If there are no replicates for predose Day 1, then the mean of the replicates from Screening will be used.

The number and proportion of participants whose QTcF results or change values meet certain predefined criteria (listed below) will be summarized.

- Absolute QTcF interval > 450 msec
- Absolute QTcF interval > 480 msec
- Absolute QTcF interval > 500 msec
- Changes from baseline QTcF >30 msec
- Changes from baseline QTcF > 60 msec

A listing of both qualitative and quantitative ECG data will be presented.

5.7.5. Neurological Examination

The neurological examinations include cranial nerves, motor, reflexes, cerebellar function, and mental status (MMSE in Part 1).

For cranial nerves/cerebellar function, a frequency table will be created for the tests of nystagmus, gait, and tremor. The number of participants with the outcomes (Absent, Present, or Not Done for the test of nystagmus, gait, and tremor, and Abnormal, Normal, or Not Done for other tests) will be summarized by treatment group and visit.

CONFIDENTIAL

The information contained herein may not be used, disclosed, or published without the written consent of Biogen MA Inc.

For reflexes examination, a frequency table will also be created for the tests of Hoffman signs and plantar response. The number of participants with the outcomes (Absent, Present, Not Done for Hoffman signs and Flexor/Extensor/Undetermined for plantar response) will be summarized by treatment group and visit. For other tests, a figure on mean scores (0=Absent, 1=Trace, 2=Normal, 3=Brisk, 4=Non-sustained clonus, 5=Sustained clonus) will be plotted versus visit. In addition, the proportion of participants with hypo-reflexia (scores 0 or 1) or apparent hyper-reflexia (scores of 3 or 4 or 5) will be summarized and the corresponding figure will also be generated.

For motor examination, a figure on mean scores vs. visit will be generated by treatment group.

Summary statistics for actual values and change from baseline of the total score of MMSE will be presented for each visit by treatment group. When there are multiple assessments during a single visit, the minimal value will be taken as the value for that visit. A listing of MMSE data will also be provided.

Neurological examinations will be presented in listings as well.

5.7.6. Columbia Suicide Severity Rating Scale (C-SSRS)

The details of derivation and imputation for C-SSRS is described in Appendix 2. The following analyses on C-SSRS measurements will be conducted.

- Descriptive summary of participants who answered “Yes” to any question 1-12 as well as participants who had suicidal ideation or suicidal behavior at baseline and at any post-baseline visit. The denominator for baseline summary is the number of participants who were dosed and had baseline assessment; the denominator for post-baseline summary is the number of participants who were dosed and had at least one post-baseline assessment for each question.
- Descriptive summary of participants who had treatment-emergent suicidal ideation, participants who had new suicidal ideation as well as participants who had worsening suicidal ideation. The denominator is the number of dosed participants with both baseline and at least one post-baseline suicidal ideation assessment.
- Descriptive summary of participants who had treatment-emergent suicidal behavior. The denominator is the number of participants who answered “No” to all suicidal behavior questions at baseline and had at least one post-baseline suicidal behavior assessment.

Listing of participants having treatment-emergent suicidal ideation will be provided. Participants who had new suicidal ideation and participants who had worsening suicidal ideation will be flagged. The listing will display both baseline and post-baseline Suicidal Ideation Scores for each participant. Listing of participants having treatment-emergent suicidal behavior will also be provided.

CONFIDENTIAL

The information contained herein may not be used, disclosed, or published without the written consent of Biogen MA Inc.

5.8. Pharmacokinetic Endpoints

The PK population will be used for the analyses of the PK data.

For the PK analysis, the serum and CSF BIIB105 concentrations will be listed and summary statistics (n, mean, SD, median, range, geometric mean and coefficient variation of geometric mean) will be presented by time for each visit. Plots of arithmetic and geometric mean concentration of serum and CSF BIIB105 versus time will be provided. Values below limit of quantitation (BLQ) prior to first dosing will be set to 0 and other BLQ will be set to half of lower limit of quantitation (LLOQ). The LLOQs are 1 ng/mL and 0.25 ng/mL for serum PK and CSF PK, respectively.

Non-compartmental analyses will be conducted by the Clinical Pharmacology and Pharmacometric group or their designate and the calculated PK parameters will be provided to Biostatistics. Summary statistics (n, mean, SD, CV%, median, range, geometric mean, CV% of geometric mean) will also be provided, if applicable, for serum PK parameters of AUC_{∞} , AUC_{last} , C_{max} , T_{max} , and $t_{1/2}$ for Days 1, 15, 29, 57, 85 for Cohorts A, B, C1 and C2. The PK parameters for Cohorts D1 and D2 will be estimated for Days 1, 15, 29, 57, 86, 114, 142, and 169. Additional PK parameters may be calculated at the discretion of the Pharmacokinetic scientist. Listing of serum PK parameters will also be generated.

PK data will be summarized by dose level in Part 1 (BIIB105-treated 5 mg [Cohort A], 20 mg [Cohort B], 60 mg [Cohorts C1 + C2], and 120 mg [Cohorts D1 + D2]).

5.9. Pharmacodynamic Endpoints

General Considerations

The PD population will be used for the analyses of the PD data. The following PD markers and biomarkers will be assessed:

- CSF ATXN2
- Plasma NfL

Other PD markers or biomarkers that may be available will be analyzed similarly to those listed above if appropriate.

BLQ values will be set as half of LLOQ in the analysis, if applicable. ND (not detectable), TNP (test not performed), and QNS (quantity not sufficient) values will be set to missing in the analysis. [REDACTED] and the LLOQ for plasma NfL is 1.38 pg/mL.

Missing data at each visit will be imputed using multiple imputation.

For analyses of Part 1, data will be analyzed in a similar way as specified for [REDACTED]

CONFIDENTIAL

The information contained herein may not be used, disclosed, or published without the written consent of Biogen MA Inc.

Sensitivity analyses will be performed by excluding potential outliers. All records from subjects whose baseline was identified as outliers will also be excluded from this sensitivity analyses as well.

Descriptive Statistics

Descriptive statistics for each PD biomarker at each visit for observed values and ratio to baseline will be summarized by treatment group. The summary statistics will include arithmetic mean along with SD, 1st and 3rd quartiles, median and range as well as the geometric mean (for observed values) or geometric mean ratio (for ratio to baseline) with the corresponding standard errors. The geometric mean and geometric mean ratio will be obtained by back-transforming means and change from baseline on natural logarithmically transformed data.

Spaghetti plot will be presented by dose level.

In addition to the analyses above the following plots over time will be presented for each biomarker as appropriate:

- Arithmetic mean ratio to baseline with standard error bars
- Geometric mean ratio to baseline with standard error bars

Missing Data

For each of the PD biomarkers, any missing postbaseline will be imputed using multiple imputation (MI). Baseline will not be imputed. The MI model will be performed based on log transformed data for each PD biomarker using the methods described in clinical function section. There will be no resetting of imputed values. The seed used for each PD biomarker is given in Table 12. Before running the model, the dataset will be sorted by cohorts and treatment group and by USUBJID.

CONFIDENTIAL

The information contained herein may not be used, disclosed, or published without the written consent of Biogen MA Inc.

Table 13: Seed used for each PD endpoint in MI

Endpoint	Seed
Plasma NfL	3847243

Statistical Analyses

For the statistical analysis of PD biomarkers, the data will be transformed using the natural logarithmic scale.

The following statistical analyses will be evaluated in PD population:

For analyses of Part 1, ANCOVA model will be performed for BIIB105 60 mg vs. Pooled Placebo 1+2 and BIIB105 120 mg vs. Pooled Placebo 1+2.

An ANCOVA model for log ratio to baseline will be performed on change from baseline values on log scale (i.e. $\log(\text{postbaseline}) - \log(\text{baseline})$) for each of the 100 imputed datasets for each PD biomarker. The model will include covariates for the corresponding baseline value, i.e. log value, baseline disease duration since symptom onset, and use of riluzole or edaravone. The least square (LS), i.e. adjusted mean of each treatment group, as well as the treatment group differences will be presented with 95% confidence intervals (CIs) and the p-value.

The following plots over time will be presented for each PD biomarker using the MI imputed datasets where appropriate:

- Arithmetic mean ratio to baseline with standard error bars
- Geometric mean ratio to baseline with standard error bars

Listing of individual data will also be provided.

CONFIDENTIAL

The information contained herein may not be used, disclosed, or published without the written consent of Biogen MA Inc.

CONFIDENTIAL

CONFIDENTIAL

CONFIDENTIAL

CONFIDENTIAL

6. Changes from Protocol-Specified Analyses

- As we do not expect to see many events during the 6 month period, we remove the time to event analyses since symptom onset.

7. References

Protocol 275AS101 Protocol Version 5.0

275AS101 Unblinding Plan Version x.0

CONFIDENTIAL

The information contained herein may not be used, disclosed, or published without the written consent of
Biogen MA Inc.

[REDACTED]

[REDACTED]

[REDACTED]

CONFIDENTIAL

The information contained herein may not be used, disclosed, or published without the written consent of
Biogen MA Inc.

APPENDICES

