4. STUDY OBJECTIVES AND ENDPOINTS

Part 1

Primary Objective	Primary Endpoint	
To evaluate the safety and tolerability of BIIB105 in participants with ALS or polyQ-ALS.	Incidence of AEs and SAEs in Part 1.	
Secondary Objective	Secondary Endpoints	
To assess the PK profile of BIIB105 in serum and CSF of participants with ALS or polyQ-ALS.	Serum and CSF concentrations of BIIB105 in Part 1. To evaluate the following serum PK parameters in Part 1:	
To evaluate the biomarker effect of BIIB105 in participants with ALS or polyQ-ALS.	Secondary biomarker measure: • Changes from baseline in plasma levels of NfL in Part 1	
Exploratory Objectives	Exploratory Endpoints	
To evaluate the PD effect of BIIB105 in participants with ALS or polyQ-ALS.	 Exploratory PD measure: Change from baseline in CSF levels of ATXN2 protein in Part 1. 	

Part 2

Primary Objective	Part 2 Primary Endpoint
To evaluate the long-term safety and tolerability of BIIB105 in participants with ALS or polyQ-ALS.	Incidence of AEs and SAEs in Part 2.

Integrated Part 1 and Part 2

Primary Objective	Primary Endpoint
To evaluate the long-term safety and tolerability of BIIB105 in participants with ALS or polyQ-ALS.	Incidence of AEs and SAEs during the BIIB105-treated period in Part 1 and/or Part 2.
Secondary Objective	Secondary Endpoints
To assess the long-term PK profile of BIIB105 in serum and CSF of participants with ALS or polyQ-ALS.	Serum and CSF concentrations of BIIB105 in Part 1 and Part 2. CSF trough PK concentration Serum PK concentration if available
To evaluate the long-term biomarker effect of BIIB105 in participants with ALS or polyQ-ALS, and, where relevant, to assess the impact of earlier initiation of BIIB105 (i.e., at start of Part 1) compared with delayed initiation of BIIB105 (i.e., at start of Part 2) on biomarkers.	• Changes from Part 1 baseline (Cohorts D1, D2) or Part 2 baseline (Cohorts A, B, C1, C2) in plasma levels of NfL

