Missing data for postbaseline assessments will be imputed using the multiple imputation method [Schafer 1997, Schafer 1999]. Visit windowing as described in Section 4.5 will be applied prior to any imputations. Any imputation on an item level within a scale will be performed prior to performing MI.

MI will be performed on actual values, domains, total scores or summary scores depending on the endpoint and not performed at the item level; the complete datasets can then be used to calculate change from baseline.

All available data will be used where subjects have missed doses but continued to perform assessments; otherwise any missing values will be imputed using MI. The Markov Chain Monte Carlo (MCMC) will be used to impute the missing postbaseline scores in the endpoint by treatment group.

Prior to performing multiple imputation, the dataset will be sorted by ascending unique subject identifier (USUBJID). The treatment variable will be coded so that early-start BIIB105 120 mg is set to 0 and placebo/delayed-start BIIB105 120 mg is set to 1 for inclusion in the MI model. Similarly, two level riluzole/edaravone use will be set to 0 for

CONFIDENTIAL

The information contained herein may not be used, disclosed, or published without the written consent of
Biogen MA Inc.

no use (i.e. neither riluzole or edaravone) and 1 for use of either riluzole or edaravone or both. When three level riluzole/edaravone use is used, two binary variables (edaril3cat1 and edaril3cat2) will be coded, where both variables will be set to 0 for no use (i.e. neither riluzole or edaravone), edaril3cat1 is set to 1 and edaril3cat2 is set to 0 for use of riluzole only, and edaril3cat1 is set to 0 and edaril3cat2 is set to 1 for edaravone use. The variable list in the model for imputations will include treatment group, riluzole/edaravone use, the corresponding baseline value for the endpoint, and all available postbaseline values. The MI model will be performed by treatment group. A set of 100 complete imputed datasets will be generated. This number of imputed datasets needs to be large enough for applying the multiple imputation method in this study as the sample size is small. The relative efficiency parameter will also be checked to determine the acceptability of the imputed results i.e. it should be close to 98% or higher. The seed used for the multiple imputation is specified in [Table 2](#).

Table 2: Seed used for each endpoint in MI

Endpoint	Seed

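### Part 1 SAP 5.9 sets not-detectable results to missing and imputes them without an upper bound, so the CSF ATXN2 estimate can be biased in either direction

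*SAP*

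**What the plan says.** Part 1 SAP 5.9 names CSF ATXN2 and plasma NfL as the PD markers and gives two rules for results at the low end of an assay:

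- A detected result too low to quantify is kept by substitution: "BLQ values will be set as half of LLOQ in the analysis, if applicable"
- A result with no detected analyte is dropped, together with samples that gave no result at all: "ND (not detectable), TNP (test not performed), and QNS (quantity not sufficient) values will be set to missing in the analysis"

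It then says "Missing data at each visit will be imputed using multiple imputation". On method: "The MI model will be performed based on log transformed data for each PD biomarker using the methods described in clinical function section", with "There will be no resetting of imputed values" and "Baseline will not be imputed". The clinical function section of the Part 1 SAP is largely redacted. The counterpart in the Part 2/integrated SAP (5.6.1) uses MCMC and adds "The MI model will be performed by treatment group".

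No left-censored model or bounded draw is visible, and the only visible PD sensitivity analysis excludes outliers. Protocol section 4 lists "Change from baseline in CSF levels of ATXN2 protein in Part 1" as an exploratory PD measure.

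**The concern.** TNP and QNS mean that no result exists. ND, on its plain meaning, is a result: the analyte was too low to detect. The plan ranks these backwards, because a low value is kept as low while a still lower one is treated as never measured. The imputation model then learns from detectable values and may place the ND sample above the detection limit.

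BIIB105 is designed to lower ATXN2 protein, and Protocol Table 4 has a column for the predicted CSF decrease at each dose (values not visible). ND results, if they occur, would plausibly be more common on active drug, so missingness could depend on the drug effect.

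The stake is the target-engagement readout. The Part 2/integrated SAP (section 1) says the study was stopped because there was no neurofilament effect and no clinical benefit. Whether the target was lowered, and by how much, matters for reading that result. The same SAP (5.9) prespecifies no further PD analysis, so the Part 1 rule is the one that applies.

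**Working it through.** The documents give no ND rate, ATXN2 assay limit, ATXN2 variance or ATXN2 effect size, so there is no planned figure to reproduce.

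**Inputs from the documents.** Active 120 mg: 36 + 12 = 48. All placebo: 2 + 2 + 3 + 12 + 1 + 6 = 26 (Protocol 5.3.1). Analysis: ANCOVA on log ratio to baseline, 120 mg versus Pooled Placebo 1+2 (Part 1 SAP 5.9).

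**Assumed inputs.** Log-scale SDs of 0.40 between and 0.25 within participants, total √(0.1600 + 0.0625) = 0.47. True ratio 0.50 or 0.70. ND in 5-30% of active samples. LLOQ 1 to 3 times the detection limit (LOD).

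**Step 1: the ND rule alone, nothing recovered by imputation.** Dropping the lowest share q of log-normal values multiplies the active geometric mean by exp[SD × φ(z_q)/(1 − q)]. For SD 0.5 and q = 0.10 this is exp[0.5 × 0.1755/0.90] = 1.102, so a true 0.50 becomes 0.551. Over SD 0.3-0.7 the inflation is 3-8% at 5% ND, 6-15% at 10% and 16-42% at 30%.

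**Step 2: the plan with multiple imputation.** Simulation: baseline plus five visits, multivariate-normal imputation by arm, 60 replicates per scenario, 5 imputations (the plan uses 100). LLOQ equals LOD, true ratio about 0.50:

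| ND on active | 5% | 10% | 20% | 30% |
|---|---|---|---|---|
| Full data | 0.493 | 0.501 | 0.487 | 0.498 |
| Plan | 0.505 | 0.521 | 0.531 | 0.563 |
| ND = half LLOQ | 0.482 | 0.480 | 0.448 | 0.449 |

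The mean log differences, plan minus full data, are 0.024, 0.039, 0.087 and 0.123. The plan's ratio is therefore too high by about 2%, 4%, 9% and 13%. For a true ratio of 0.70 the excess is about 2%, 4%, 6% and 9%.

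**Step 3: the plan with a BLQ band.** When LLOQ exceeds LOD, BLQ values enter at half the LLOQ. Plan estimate, full data about 0.50:

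| LLOQ/LOD | 5% ND | 10% ND | 20% ND | 30% ND |
|---|---|---|---|---|
| 1.5 | 0.460 | 0.448 | 0.442 | 0.452 |
| 2.0 | 0.441 | 0.441 | 0.475 | 0.518 |
| 3.0 | 0.475 | 0.532 | 0.620 | 0.697 |

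The sign changes: lowering is overstated at 1.5, and ranges from slightly overstated to strongly understated at 3.0.

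**Step 4: a censored-normal model.** Separate single-visit check with the same SDs and arm sizes, true ratio 0.50, ND 10/20/30%:

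| LLOQ/LOD | Plan | Censored-normal |
|---|---|---|
| 1.0 | 0.528 / 0.551 / 0.575 | 0.502 / 0.500 / 0.499 |
| 1.5 | 0.458 / 0.453 / 0.463 | 0.499 / 0.496 / 0.500 |
| 2.0 | 0.441 / 0.464 / 0.504 | 0.497 / 0.493 / 0.493 |

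At LLOQ/LOD 1.25 the plan gives 0.48-0.49. Across ratios 1 to 1.5, treating ND as half the LLOQ gives 0.44-0.49. At ratio 3 with 20-30% ND most active values are censored; there the plan gives 0.625 and 0.706, and the censored-normal model also failed.

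**The case against.** The strongest objection is that direction and size are unknown. A reader might infer from the ND rule that target engagement is understated. The documents do not support that as a general statement. They treat BLQ and ND as separate result types, which suggests an LLOQ above the detection limit, and there the half-LLOQ rule can cancel or reverse the bias. At 1.25 times the limit the plan is close to unbiased. This stands, and it limits the conclusion to bias of uncertain sign.

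The premises are also conditional. How the laboratory separates ND from BLQ is not visible, and text just before the NfL LLOQ is redacted. If every result below the LLOQ is reported as BLQ, the ND rule does nothing. The lowest concentrations need not be the largest falls from baseline, since a placebo participant with a low baseline can also be ND. The visible seed table lists only plasma NfL; rows may be redacted, and the text applies imputation to each PD biomarker.

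Two further inferences are tempting but unsupported. One is a flattened dose response, which was not examined across doses. The other is that participants with only ND results leave the PD population. Part 1 SAP 3.4 requires one available post-dose evaluation and does not say that an ND result fails this. It would also take ND at every CSF visit, seven for D1/D2 from Day 15 to Day 169.

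Finally, ATXN2 is exploratory, individual data will be listed, and no visible decision rule turns on this estimate. That lowers the priority but does not make the rule sound.

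**Conclusion.** The point holds in conditional form. The plan explicitly classes ND with samples that gave no result and imputes it without a bound, while keeping the higher BLQ results at half the LLOQ. If ND means below detection, missing-at-random imputation cannot recover those values. The ND rule alone then moves a true ratio of 0.50 to about 0.51-0.57 at 5-30% ND. With the BLQ rule added, the simulated estimates ran from 0.441 to 0.697, so the reported lowering could be too large or too small. With no ND results the rule has no effect.

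All magnitudes rest on assumed SDs, ND rates and assay limits. The consequence is confined to the exploratory ATXN2 target-engagement result, which makes this a should-fix item. No effect on the primary safety endpoint arises, and none is claimed here for plasma NfL, although the same sentence governs it.

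**What to change.** In Part 1 SAP 5.9:

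1. Take ND out of the set-to-missing sentence; keep only TNP and QNS there. Define ND and BLQ for each assay, with both limits.
2. Analyse ND and BLQ as left-censored, by a censored-normal likelihood or by imputation draws bounded above by the relevant limit. Do not simply give ND half the LLOQ: at LLOQ 1 to 1.5 times the detection limit that usually moves the error towards overstating the reduction.
3. Report ND and BLQ counts by dose and visit.

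The cost is a few lines of SAP text and a small programming change, with no new data. Since the study has already been stopped, this would in practice be run as a post hoc sensitivity analysis and labelled so. The limitation is that a censored model becomes unreliable when most active values are below a limit; the counts in item 3 show whether that applies.
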